6.8 Follow-Up

Subjects who discontinue treatment for any reason will be followed for disease progression and overall survival. At treatment discontinuation, subjects will undergo a safety assessment approximately 30 days post the last dose of study drug. In addition off study evaluations per the Schedule of Assessments, Section 2 will be done. If the subject is in remission for more than 1 year then follow-up will be every four months unless there are clinical indications.

Patients will be followed for survival every three months.

6.9 On Study Evaluations

All study evaluations outlined in schedule 2 of Assessments will be completed during study for assessments of response and toxicity.

Study visits and procedures may be scheduled +/- 3 days window except for screening and cycle one.

CT scans should include neck if necessary

If in CR by radiologic evaluation, bone marrow biopsy and PET scan, colonoscopy or endoscopy with random biopsy may be necessary to confirm CR.

After CR has been confirmed by a repeat scan, the restaging scans will be obtained every four cycles, unless deemed clinically necessary by treating physician.

7 Adverse events

7.0 Serious Adverse Event (SAE) Definition

 □ Results in death □ Is life-threatening¹ □ Requires inpatient hospitalization or prolongation of existing hospitalizatio □ Results in persistent or significant disability or incapacity² □ Is a congenital anomaly or birth defect □ Is an important medical event³ 	A serious adverse event is one that at any dose (including overdose):			
Requires inpatient hospitalization or prolongation of existing hospitalizatio Results in persistent or significant disability or incapacity ² Is a congenital anomaly or birth defect		Results in death		
Results in persistent or significant disability or incapacity ² Is a congenital anomaly or birth defect		Is life-threatening ¹		
☐ Is a congenital anomaly or birth defect		Requires inpatient hospitalization or prolongation of existing hospitalization		
		Results in persistent or significant disability or incapacity ²		
☐ Is an important medical event ³		Is a congenital anomaly or birth defect		
		Is an important medical event ³		

¹ "Life-threatening" means that the subject was at immediate risk of death at the time of the serious adverse event; it does not refer to a serious adverse event that hypothetically might have caused death if it were more severe.

^{2&}quot;Persistent or significant disability or incapacity" means that there is a substantial disruption of a person's ability to carry out normal life functions.

³Medical and scientific judgment should be exercised in deciding whether expedited reporting is appropriate in situations where none of the outcomes listed above occurred. Important medical events that may not be immediately life-threatening or result in death or hospitalization but may jeopardize the patient or may require intervention to prevent one of the other outcomes listed in the definition above should also usually be considered serious. Examples of such events include allergic bronchospasm requiring intensive treatment in an emergency room or at

home, blood dyscrasias or convulsions that do not result in inpatient hospitalization, or the development of drug dependency or drug abuse. A new diagnosis of cancer during the course of a treatment should be considered as medically important.

7.1 Adverse Event Reporting

Toxicity will be scored using CTCAE Version 4.0 for toxicity and adverse event reporting. A copy of the CTCAE Version 4.0 can be downloaded from the CTEP homepage (http://evs.nci.nih.gov/ftp1/CTCAE/About.html). All appropriate treatment areas have access to a copy of the CTCAE Version 4.0. All adverse clinical experiences, whether observed by the investigator or reported by the patient, must be recorded, with details about the duration and intensity of each episode, the action taken with respect to the test drug, and the patient's outcome. The investigator must evaluate each adverse experience for its relationship to the test drug and for its seriousness.

The investigator must appraise all abnormal laboratory results for their clinical significance. If any abnormal laboratory result is considered clinically significant, the investigator must provide details about the action taken with respect to the test drug and about the patient's outcome.

Second primary malignancies are considered events of interest and should be included as part of the assessment of adverse events throughout the course of the study. Investigators are to report any second primary malignancies as serious adverse events regardless of causal relationship to lenalidomide, occurring at any time for the duration of the study For all subjects who develop second primary malignancies, sites will be required to submit all diagnostic reports (eg pathology, cytogenetics, flow cytometry results) from the indication diagnostic confirmation samples submitted at screening and all reports for the tumor samples from the SPM diagnosis. For SPMs diagnosed at another institution (outside the investigational site), sites are to make every effort to obtain these reports for the SPM confirmation.

Pregnancies

Pregnancies and suspected pregnancies (including a positive pregnancy test regardless of age or disease state) of a female subject occurring while the subject is on lenalidomide, or within 28 days of the subject's last dose of lenalidomide, are considered immediately reportable events. Lenalidomide is to be discontinued immediately. The pregnancy, suspected pregnancy, or positive pregnancy test must be reported to Celgene Drug Safety immediately by facsimile or email using the Pregnancy Initial Report Form. The female subject should be referred to an obstetrician-gynecologist, preferably one experienced in reproductive toxicity for further evaluation and counseling.

The Investigator will follow the female subject until completion of the pregnancy, and must notify Celgene Drug Safety immediately about the outcome of the pregnancy (either normal or abnormal outcome) using the Pregnancy Follow-up Report Form. If the outcome of the pregnancy was abnormal (e.g., spontaneous or therapeutic abortion), the Investigator should report the abnormal outcome as an AE. If the abnormal outcome meets any of the serious criteria, it must be reported as an SAE to Celgene Drug Safety immediately by facsimile, or

other appropriate method, within 24 hours of the Investigator's knowledge of the event using the SAE Report Form,

All neonatal deaths that occur within 28 days of birth should be reported, without regard to causality, as SAEs. In addition, any infant death after 28 days that the Investigator suspects is related to the *in utero* exposure to the study drug should also be reported to Celgene Drug Safety immediately by facsimile, or other appropriate method, within 24 hours of the Investigator's knowledge of the event using the SAE Report Form.

Male Subjects

If a female partner of a male subject taking investigational product becomes pregnant, the male subject taking lenalidomide should notify the Investigator, and the pregnant female partner should be advised to call their healthcare provider immediately.

7.2 Investigator Reporting Responsibilities

The conduct of the study will comply with all FDA safety reporting requirements.

IND Annual Reports

If the FDA has granted an IND number, it is a requirement of 21 CFR 312.33, that an annual report is provided to the FDA within 60-days of the IND anniversary date. 21 CRF 312.33 provides the data elements that are to be submitted in the report. The Annual Report should be filed in the study's Regulatory Binder, and a copy provided to Celgene Corporation as a supporter of this study as follows.

Celgene Corporation Attn: Medical Affairs Operations [name]

All adverse experience reports must include the patient number, age, sex, weight, severity of reaction (mild, moderate, severe), relationship to study drug (probably related, unknown relationship, definitely not related), date and time of administration of test medications and all concomitant medications, and medical treatment provided. The investigator is responsible for evaluating all adverse events to determine whether criteria for "serious" and as defined above are present. The investigator is responsible for reporting adverse events to Celgene as described below.

7.2.1 Expedited Reporting by Investigator to Celgene

Serious adverse events (SAE) are defined above. The investigator should inform Celgene in writing using a Celgene SAE form or MEDWATCH 3500A form of any SAE within 24 hours of being aware of the event. The written report must be completed and supplied to Celgene by facsimile within 24 hours/1 business day. The initial report must be as complete as possible, including an assessment of the causal relationship between the event and the investigational product(s). Information not available at the time of the initial report (e.g., an end date for the adverse event or laboratory values received after the report) must be documented on a follow-up report. A final report to document resolution of the SAE is required. The Celgene tracking number (RV-NHL-PI-0488) and the institutional protocol number should be included on SAE reports (or on the fax cover letter) sent to Celgene. A copy of the fax transmission confirmation of the SAE report to Celgene should be attached to the SAE and retained with the patient records.

Participating study sites must report SAEs to Celgene as described and within 24 hours of awareness. Participating sites should also report SAEs to the primary study site.

7.2.2 Report of Adverse Events to the Institutional Review Board

The Principal Investigator is required to notify his/her Institutional Review Board (IRB) of a serious adverse event according to institutional policy.

7.2.3 Investigator Reporting to the FDA

Serious adverse events (SAEs) that are unlisted/unexpected, and at least possibly associated to the drug, and that have not previously been reported in the Investigators brochure, or reference safety information document should be reported promptly to the Food and Drug Administration (FDA) by telephone or fax. Fatal or life threatening SAEs that meet the criteria for reporting to the FDA must be reported to the FDA within 7 calendar days after awareness of the event. All other SAEs that meet the criteria for reporting to the FDA must be reported to the FDA within 15 calendar days after awareness of the event. A clear description of the suspected reaction should be provided along with an assessment as to whether the event is drug or disease related.

Participating study sites should NOT report SAEs to the FDA. Rather, participating sites should report SAEs to Celgene and the primary study site, and the primary site will be responsible for reporting to FDA.

Adverse event updates/IND safety reports

Celgene shall notify the Investigator via an IND Safety Report of the following information:

- Any AE associated with the use of study drug in this study or in other studies that is both serious and unexpected.
- Any finding from tests in laboratory animals that suggests a significant risk for human subjects including reports of mutagenicity, teratogenicity, or carcinogenicity.

The Investigator shall notify his/her IRB/EC promptly of these new serious and unexpected AE(s) or significant risks to subjects.

The Investigator must keep copies of all AE information, including correspondence with Celgene and the IRB/EC, on file (see Section 12.4 for records retention information).

8 Response Criteria

Responses will be assessed by Revised Working Group Response Criteria for Malignant Lymphoma (Cheson et al, JCO Vol 25, No 5 (February 10), 2007: pp. 579-586), as follows:

8.1 Complete Response (CR):

- 1. Complete disappearance of all detectable clinical evidence of disease and disease-related symptoms if present before therapy.
- 2a. Typically FDG-avid lymphoma: in patients with no pretreatment PET scan or when the PET scan was positive before therapy, a post-treatment residual mass of any size is permitted as long as it is PET negative.
- 2b. Variably FDG-avid lymphomas/FDG avidity unknown: in patients without a pretreatment PET scan, or if a pretreatment PET scan was negative, all lymph nodes and nodal masses must have regressed on CT to normal size (≤ 1.5 cm in their greatest transverse diameter for nodes > 1.5 cm before therapy). Previously involved nodes that were 1.1 to 1.5 cm in their long axis and more than 1.0 cm in their short axis before treatment must have decreased to ≤ 1.0cmin their short axis after treatment.
- 2. The spleen and/or liver, if considered enlarged before therapy on the basis of a physical examination or CT scan, should not be palpable on physical examination and should be considered normal size by imaging studies, and nodules related to lymphoma should disappear. However, determination of splenic involvement is not always reliable because a spleen considered normal in size may still contain lymphoma, whereas an enlarged spleen may reflect variations in anatomy, blood volume, the use of hematopoietic growth factors, or causes other than lymphoma.
- 3. If the bone marrow was involved by lymphoma before treatment, the infiltrate must have cleared on repeat bone marrow biopsy. The biopsy sample on which this determination is made must be adequate (with a goal of > 20 mm unilateral core). If the sample is indeterminate by morphology, it should be negative by immunohistochemistry. A sample that is negative by immunohistochemistry but that demonstrates a small population of clonal lymphocytes by flow cytometry will be considered a CR until data become available demonstrating a clear difference in patient outcome.

8.2 Complete Response Unconfirmed (CRu):

The use of the above definition for CR and that below for PR eliminates the category of CRu.

8.3 Partial Response (PR)

- 1. At least a 50% decrease in sum of the product of the diameters (SPD) of up to six of the largest dominant nodes or nodal masses. These nodes or masses should be selected according to all of the following: they should be clearly measurable in at least 2 perpendicular dimensions; if possible they should be from disparate regions of the body; and they should include mediastinal and retroperitoneal areas of disease whenever these sites are involved.
- 2. No increase should be observed in the size of other nodes, liver, or spleen.
- 3. Splenic and hepatic nodules must regress by $\geq 50\%$ in their SPD or, for single nodules, in the greatest transverse diameter.
- 4. With the exception of splenic and hepatic nodules, involvement of other organs is usually assessable and no measurable disease should be present.
- 5. Bone marrow assessment is irrelevant for determination of a PR if the sample was positive before treatment. However, if positive, the cell type should be specified (eg, large-cell lymphoma or small neoplastic B cells). Patients who achieve a CR by the above criteria, but who have persistent morphologic bone marrow involvement will be considered partial responders. When the bone marrow was involved before therapy and a clinical CR was achieved, but with no bone marrow assessment after treatment, patients should be considered partial responders.
- 6. No new sites of disease should be observed.
- 7. Typically FDG-avid lymphoma: for patients with no pretreatment PET scan or if the PET scan was positive before therapy, the post-treatment PET should be positive in at least one previously involved site.
- 8. Variably FDG-avid lymphomas/FDG-avidity unknown: for patients without a pretreatment PET scan, or if a pretreatment PET scan was negative, CT criteria should be used. In patients with follicular lymphomaor mantle-cell lymphoma, a PET scan is only indicated with one or at most two residual masses that have regressed by more than 50% on CT; those with more than two residual lesions are unlikely to be PET negative and should be considered partial responders.

8.4 Stable disease (SD):

- 1. A patient is considered to have SD when he or she fails to attain the criteria needed for a CR or PR, but does not fulfill those for progressive disease (see Relapsed Disease [after CR]/Progressive Disease [after PR, SD]).
- 2. Typically FGD-avid lymphomas: the PET should be positive at prior sites of disease with no new areas of involvement on the post treatment CT or PET.

3. Variably FDG-avid lymphomas/FDG-avidity unknown: for patients without a pretreatment PET scan or if the pretreatment PET was negative, there must be no change in the size of the previous lesions on the post-treatment CT scan.

8.5 Relapsed Disease (after CR)/Progressive Disease (after PR, SD)

Lymph nodes should be considered abnormal if the long axis is more than 1.5 cm regardless of the short axis. If a lymph node has a long axis of 1.1 to 1.5 cm, it should only be considered abnormal if its short axis is more than 1.0. Lymph nodes ≤1.0 ≤1.0cm will not be considered as abnormal for relapse or progressive disease.

- 1. Appearance of any new lesion more than 1.5 cm in any axis during or at the end of therapy, even if other lesions are decreasing in size. Increased FDG uptake in a previously unaffected site should only be considered relapsed or progressive disease after confirmation with other modalities. In patients with no prior history of pulmonary lymphoma, new lung nodules identified by CT are mostly benign. Thus, a therapeutic decision should not be made solely on the basis of the PET without histologic confirmation.
- 2. At least a 50% increase from nadir in the SPD of any previously involved nodes, or in a single involved node, or the size of other lesions (eg, splenic or hepatic nodules). To be considered progressive disease, a lymph node with a diameter of the short axis of less than 1.0cm must increase by ≥ 50% and to a size of 1.5x1.5 cm or more than 1.5 cm in the long axis.
- 3. At least a 50% increase in the longest diameter of any single previously identified node more than 1 cm in its short axis.
- 4. Lesions should be PET positive if observed in a typical FDG avid lymphoma or the lesion was PET positive before therapy unless the lesion is too small to be detected with current PET systems (<1.5 cm in its long axis by CT).

Measurable extranodal disease should be assessed in a manner similar to that for nodal disease. For these recommendations, the spleen is considered nodal disease. Disease that is only assessable (eg, pleural effusions, bone lesions) will be recorded as present or absent only, unless, while an abnormality is still noted by imaging studies or physical examination, it is found to be histologically negative.

8.6 Progressive disease (PD) in PR patients or nonresponders

- ≥50 % increase from nadir in the SPD of any previously identified abnormal node for PRs or nonresponders.
- Appearance of any new lesion during or at the end of therapy.

Summary of response criteria:

Response	Definition			
Category		Nodal Mass	Spleen, Liver	Bone Marrow
Category				
CR	Disappearance of all evidence of disease	(a) FDG-avid or PET positive prior to therapy; mass of any size permitted if PET negative (b) Variably FDG-avid or PET negative; regression to normal size on CT	Not palpable, nodules disappeared	Infiltrate cleared on repeat biopsy; if indeterminate by morphology, immunohistochemistry should be negative
PR	Regression of measurable disease and no new sites	≥ 50% decrease in SPD of up to 6 largest dominant masses; no increase in size of other nodes (a) FDG-avid or PET positive prior to therapy; one or more PET positive at previously involved site (b) Variably FDG-avid or PET negative; regression on CT	≥50% decrease in SPD of nodules (for single nodule in greates transverse diameter); no increase in size of liver or spleen	Irrelevant
SD	Failure to attain CR/PR or PD	(a) FDG-avid or PET positive prior to therapy; PET positive at prior sites of disease and no new sites on CT or PET		

Response Category	Definition	Nodal Mass	Spleen, Liver	Bone Marrow
		(b) Variably FDG-avid or PET negative; no change in size of previous lesions on CT		
Relapse/PD	Any new lesion or increase by _≥ 50% of previously involved sites from nadir	Appearance of a new lesion(s) >1.5 cm in any axis, ≥ 50% increase in SPD of more than one node, Or ≥ 50% increase in longest diameter of a previously identified node >1 cm in short axis Lesions PET positive if FDG-avid lymphoma or PET positive	> 50 increase from nadir in the SPD of any previous lesions	New or recurrent involvement

8.7 Duration of Overall Response:

The duration of overall response is measured from the time measurement criteria are met for CR/PR (whichever status is recorded first) until the first date that recurrent or progressive disease is objectively documented (taking as reference for progressive disease the smallest measurements recorded since the treatment started).

The duration of overall complete response is measured from the time measurement criteria are first met for CR until the first date that recurrent disease is objectively documented.

8.7.1 Duration of Stable Disease:

Stable disease is measured from the start of the treatment until the criteria for disease progression are met, taking as reference the smallest measurements recorded since the treatment started.

The clinical relevance of the duration of SD varies for different tumor types and grades. Therefore, it is highly recommended that the protocol specify the minimal time interval required between two measurements for determination of SD. This time interval should take into account the expected clinical benefit that such a status may bring to the population under study.

8.7.2 Time to Progression:

Time to progression will be measured as the time from when the patient started treatment to the time the patient is first recorded as having disease progression, or the date of death if the patient dies due to causes other than disease progression.

8.7.3 Time to Treatment Failure:

Time to treatment failure will be measured as the time from when the patient started treatment to the time the patient is withdrawn due to: adverse events, progressive disease/insufficient therapeutic response, death, failure to return, and refused treatment/did not cooperate/withdrew consent. The date of last dose of treatment will be used as the date of event in the case that PD was not recorded earlier.

8.7.4 Survival:

Survival will be measured as the time from start of treatment to the date of death or the last date the patient was known to be alive.

9 **Data Management**

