Lenalidomide is currently approved by the FDA for multiple myeloma and myelodysplastic syndrome and is being studied in other hematological conditions including lymphomas. Although the exact anti-tumor mechanism of action of lenalidomide is unknown, a number of mechanisms are postulated to be responsible for lenalidomide's anti-tumor activity. In laboratory models, lenalidomide can enhance T- and NK-cell synapse formation with tumor B cells to enhance immune-mediated cytotoxicity. Lenalidomide has also been shown to reverse the impaired ability of T cells to form immunological synapses, a process that appears to be defective in lymphomas

and leukemias. Lenalidomide also exerts antiproliferative activity via upregulation of tumor-suppressor genes (including p21 and SPARC) that results in G1 cell-cycle arrest, caspase activation, and apoptosis.

Multiple clinical studies have established that lenalidomide is a promising agent in the treatment of lymphomas. NHL-003 study by Czuczman et al evaluated the role of lenalidomide as monotherapy in 217 patients with relapsed/refractory aggressive Non-Hodgkin's Lymphoma. Among these, 50% patients had Diffuse large B cell Lymphoma, 26% Mantle Cell Lymphoma, 9% Follicular

Lymphoma Grade III, and 15% transformed lymphoma. The ORR for all 217 patients was 35%, with 13% complete response, 22% partial response, and 21% had stable disease. Responses were observed in all histological types. Median progression-free survival for all patients was 3.5 months and the median duration of response for the 77 responders was 11.6 months. The primary side effect of lenalidomide was reversible myelosuppression.

The efficacy and safety of lenalidomide was also shown in relapsed/refractory mantle cell lymphoma [3,4, 5]. Czuczman et al evaluated lenalidomide monotherapy with an overall response rate of 41%. Zaja et al studied lenalidomide in combination with dexamethasone, with a 50% overall response rate. Wang et al reported an overall response rate of 53% for the combination of lenalidomide with rituximab. These studies also demonstrated a favorable toxicity profile for lenalidomide and the combinations.

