4.1 Introduction

Despite the availability of multiple therapeutic modalities and a high response rate to initial therapy, most patients with low grade non-Hodgkin lymphoma (NHL) will develop recurrent or refractory disease and most ultimately die from lymphoma-related complications. Chemotherapy and radiation therapy have clearly provided benefit to patients with these disorders. It is evident, however, that these agents are limited in their potential for cure of patients with indolent lymphoma, and thus new approaches are under investigation. The monoclonal antibody rituximab (directed against the B-cell antigen CD20) has been shown to be useful in the treatment of relapsed patients with low grade NHL for which it received Food and Drug Administration (FDA) approval. In a pivotal trial of 166 patients with relapsed low grade NHL, a response rate of 48% was observed (approximately 60% in the follicular histologies), with a median time to progression (TTP) of 12 months in responders. A higher response rate was observed in patients receiving rituximab as second-line therapy (compared to those patients following three or more prior chemotherapy regimens). In low-grade NHL patients who initially respond (time to progression of at least 6 months) and then relapse after single agent rituximab therapy, an overall response rate of 40% has been reported following retreatment, with median TTP of about 18 months after the second administration. Subsequent studies of rituximab have evaluated its utility as a single agent in various other subtypes of NHL, such as diffuse large B-cell and mantle cell, as well as in combination with numerous chemotherapy regimens. Rituximab has been widely adopted by oncologists as a well-tolerated and active agent in NHL, and most lymphoma patients receive it at some point in their course either as a single agent, or in combination with chemotherapy.

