5.2.2 Secondary Endpoints

• Time to disease progression

- Tolerability (type, frequency, severity and relationship of adverse events to study treatment based on the NCI criteria)
- Duration of response from the start of therapy
- Overall survival
- Serum cytokine levels
- Tumor Control Rate

Investigational Plan

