11.2 Datasets to be analyzed

The primary study endpoint is response to therapy (defined as a CR, nCR, or PR of 4 months). The secondary end points (time to progression, tolerability, duration of response and overall survival will be measured from the time of entry into the clinical trial.

Toxicity information recorded will include the type, severity, time of onset, time of resolution, and the probable association with the study regimen. Tables will be constructed to summarize the observed incidence by severity and type of toxicity.

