11.3 Statistical Methodology

30 patients will be treated with rituximab and lenalidomide at indicated dose levels. Objective response (CR +PR) will be monitored using Simon's optimal 2-stage design. This study design is optimal in that sense that it minimizes the expected sample size among competing designs. The OR rate of rituximab naïve follicular lymphoma patients treated with rituximab alone is approximately 60%. A 20% increase in the objective response rate with the addition of lenalidomide to 80% in this treatment naïve patient population would justify evaluation of this regimen in larger, more definitive trials. We assume a one-sided type I error rate of 5% and desire at least 80% power to conclude that this regimen elicits and objective response rate significantly greater than 60% if the true response rate of this regimen is 60% or higher. Under these assumptions, if 11 or fewer OR's are observed in the first 26 patients, the principal investigator may conclude that regimen is insufficiently active to warrant further study. Otherwise, accrual will continue to a total of 30 patients. If 15 or more OR's are observed in 30 patients, this regimen will be deemed sufficiently active to warrant further study. Given the relatively small sample size the additional study in patients receiving radiation therapy would be considered exploratory. Any documented response would be considered "significant" and warrant further study.

Analysis Plan:

Continuous variables (e.g., age, hematology values) will be summarized using the mean (s.d.) or median (range). Frequency tables will be used to summarize categorical variables. Logistic regression will be used to assess the impact of patient characteristics (e.g., low/high LDH) on the objective response rate. The distribution of time-to-event endpoints (e.g., CR duration, overall survival) will be estimated using the method of Kaplan and Meier. Comparison of time-to-event endpoints by important subgroups of patients will be made using the logrank test. Cox (proportional hazards) regression will be used to evaluate multivariable predictive models of time-to-event outcomes.

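### The time-to-progression rule in Section 8.7.2 gives an end date for deaths from other causes but none for a lymphoma death without recorded progression, and no section says which deaths are events and which are censored

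*Combined protocol and SAP*

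**What the plan says.** Section 5.2.2 lists "Time to disease progression" as a secondary endpoint without defining it. The definition is in Section 8.7.2. The interval is "the time from when the patient started treatment". Its first possible end is worded "to the time the patient is first recorded as having disease progression". Section 8.7.2 then allows one alternative end, which depends on the cause of death: "or the date of death if the patient dies due to causes other than disease progression".

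The statistics sections add little. Section 11.2 says the secondary endpoints "will be measured from the time of entry into the clinical trial", which is a different start point. Section 11.3 says the distribution of time-to-event endpoints "will be estimated using the method of Kaplan and Meier" and names the logrank test and Cox regression. Neither section says what counts as an event or when a patient is censored.

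The neighbouring definitions treat death in different ways. Duration of response (8.7) ends at objectively documented recurrence or progression and is silent on death. Time to treatment failure (8.7.3) includes death whatever its cause. Survival (8.7.4) runs to death or to the date last known alive; the latter is clearly a censoring date, although it is not called one.

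PFS is not an endpoint of this trial. It appears only in the background, for cited studies (Synopsis: "Median progression-free survival for all patients was 3.5 months"), as does TTP (Section 4.1: "with a median time to progression (TTP) of 12 months in responders").

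**The concern.** A time-to-event endpoint needs every patient to have either an event date or a censoring date. Section 8.7.2 names two ways for TTP to end: recorded progression, and death from something other than progression. Under the usual meaning of TTP, the deaths to count are those from lymphoma, and other deaths are censored or treated as competing. Under PFS, all deaths count. The written rule gives an end date to the deaths that TTP would not count and none to the deaths that both TTP and PFS would count.

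At stake is what the published curve estimates. Two analysts following the same text could produce different curves from the same 30 patients, and the choice could be made after the deaths are known.

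**Working it through.** The plan gives no event count, median, target or power for TTP, so there is no figure of its own to reproduce. The check is mainly textual; the numbers below rest on assumptions.

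**Step 1. The possible readings.** Two questions are open: is an other-cause death an event or censored, and is a lymphoma death without recorded progression an event (progression taken as recorded at death) or not?

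| Other-cause death | Lymphoma death, no recorded progression | Resulting endpoint |
|---|---|---|
| Event | Not an event | Hybrid (the literal reading) |
| Event | Event | PFS under a TTP label |
| Censored | Not an event | TTP that omits lymphoma deaths |
| Censored | Event | Conventional TTP |

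The last row needs two inferences that the text does not state.

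**Step 2. Can the uncovered case arise?** The Schedule of Study Assessments calls for scans every 8 weeks on treatment and at its end. After a confirmed complete response the interval may lengthen to four cycles (4 × 28 days = 16 weeks), and after 50 cycles scans are at investigator discretion. A lymphoma death before progression is recorded is therefore possible. Section 6.8 does follow patients for progression after treatment stops, which makes it less likely.

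**Step 3. Other-cause deaths alone.** Assume all 30 patients (Section 5.3) are followed for 24 months unless they die, with 6 recorded progressions, d other-cause deaths, and no lymphoma death lacking a recorded progression.

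- Deaths counted as events: 1 − (6 + d)/30.
- Deaths censored, each contributing about half its exposure: approximately 1 − 6/(30 − d/2).

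| d | Counted | Censored | Difference |
|---|---|---|---|
| 1 | 1 − 7/30 = 76.7% | 1 − 6/29.5 = 79.7% | 3.0 points |
| 2 | 1 − 8/30 = 73.3% | 1 − 6/29 = 79.3% | 6.0 points |
| 3 | 1 − 9/30 = 70.0% | 1 − 6/28.5 = 78.9% | 8.9 points |

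The difference arises only on a reading that counts these deaths as events.

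**Step 4. Both kinds of death.** Assume independent constant hazards. For recorded progression, take ln 2/48 = 0.0144 per month (a 48-month median). For each kind of death without recorded progression, take 0.002 or 0.004 per month. Event-free probability at 24 months is exp(−24 × sum of the hazards counted as events).

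| Lymphoma / other hazard | Literal hybrid | PFS | Progression only | Conventional TTP |
|---|---|---|---|---|
| 0.004 / 0.002 | 67.4% | 61.2% | 70.7% | 64.2% |
| 0.002 / 0.004 | 64.2% | 61.2% | 70.7% | 67.4% |
| 0.002 / 0.002 | 67.4% | 64.2% | 70.7% | 67.4% |

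Against conventional TTP, the literal rule is 3.2 points too high in the first row, 3.2 points too low in the second, and equal in the third. The direction depends on which kind of death is commoner. If no lymphoma death lacks a recorded progression, the literal rule equals PFS and only the name is wrong.

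**Step 5. Start point.** Section 8.7.2 starts at treatment and Section 11.2 at trial entry, which is not defined. If entry means registration, Appendix VII allows it up to 72 hours before treatment, so the numerical effect would be negligible. The two sections still disagree.

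**The case against.** The strongest case against is that a sensible team would read the rule benignly. Section 8.7.2 never uses the word event, and Section 8.7.4 uses similar phrasing for a censoring date, so other-cause deaths may have been meant as censored. Unlike 8.7, Section 8.7.2 does not require progression to be objectively documented, so a death attributed to lymphoma could be taken as progression recorded on that day. Scans are frequent on treatment, so the uncovered case should be rare. At n = 30 the standard error of a proportion near 73% is √(0.73 × 0.27/30), about 8 points, so the differences in Step 3 are roughly one standard error or less.

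The points about rarity and size stand. The benign readings do not close the gap. Censoring other-cause deaths still leaves lymphoma deaths without a date. Treating lymphoma deaths as progression, with other deaths as events, gives PFS under the wrong name. Conventional TTP needs both inferences, and the text gives neither.

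Three stronger readings are tempting and are not supported:

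- A reader might infer that the plan censors undocumented lymphoma deaths and so biases the curve upward. The plan does not say how they are handled, and Step 4 shows that the error can go either way.
- A reader might infer that the result will be set beside the rituximab TTP figures in Section 4.1 (12 months and about 18 months). No such comparison is planned. Those figures come from relapsed patients, and the documents do not say how those studies handled deaths.
- A reader might take the background's use of both TTP and PFS as proof of a deliberate distinction here. The terms describe different cited studies and are not defined.

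**Conclusion.** The point holds as a defect of definition in a secondary endpoint. Section 8.7.2 states a rule that does not fit the endpoint it names, leaves one class of deaths without a date, and is not completed elsewhere. A reader might conclude that the endpoint is neither TTP nor PFS, but that is true only of the literal hybrid; the firm conclusion is that the text does not determine which endpoint it is.

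The practical effect is probably small. TTP has no target, power or decision rule, there are 30 patients, and the primary response endpoint and sample size are not affected. The 3 to 9 points rest on assumed counts (6 progressions, 1 to 3 other-cause deaths) and on counting those deaths as events. The hazards in Step 4 are also assumptions. The change is worth making before analysis because it is cheap and removes a choice that would otherwise be made with the data in view.

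**What to change.** Rewrite Section 8.7.2 so that the name and the events agree, in one of two ways:

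1. Call it progression-free survival, with recorded progression or death from any cause as the event.
2. Keep time to progression, with recorded progression or death from lymphoma as the event and other deaths either censored or treated as a competing event. If competing, Section 11.3 should name a cumulative incidence estimate for this endpoint in place of Kaplan-Meier.

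Under either option, state that patients without an event are censored at their last disease assessment, and give Sections 8.7.2 and 11.2 the same start point. Reporting both endpoints is optional.

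The cost is a few sentences. The first option needs only progression and death dates, which follow-up for progression and survival (Section 6.8) should already provide. The second also needs cause of death. The present rule already depends on that, but the content of the follow-up and expiration forms is not shown, so check that they record it.
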